5.0 STATISTICAL CONSIDERATIONS

This is a randomized trial to compare oral Ondansetron (OO) and Granisetron patch (GP) for control of delayed nausea and vomiting in patients undergoing chemoradiation for the treatment of locally advanced cervical, endometrial or vaginal cancer. The primary outcome is response to anti-emetic therapy (no emetic or retching episodes and no rescue medication use) in days 4-7 of the first cycle of chemotherapy.

Patients will be randomized between OO and GP using a Bayesian adaptive algorithm. (8) Technical details of this methodology are given in the "Technical Details" section below. The first 40 patients will be randomized fairly between the 2 treatment arms. Beginning with the 41st patient and as the trial progresses and data accrue the randomization will become unbalanced in favor of the therapy that, on average, has better results in terms of treatment failure, so that each successive patient is more likely to receive the treatment showing better results.

We will enroll at least 75 and at most 150 patients at an expected rate of 5 patients per month. We will enroll up to 30 patients in LBJ. With treatment OO we expect a treatment failure rate of 0.2750. (6) With treatment GP we hope to improve the treatment failure rate to 0.1375 (i.e., reduce the treatment failure rate by half).

Beginning with the 76th patient the trial will be stopped early and a treatment selected as being "superior" if the probability is 0.925 or more that one treatment's failure rate is lower than the other treatment's failure rate. If all 150 patients are enrolled, then a treatment will be selected as being "superior" if the probability is 0.915 or more that one treatment's failure rate is lower than the other treatment's failure rate. In addition, accrual to a treatment arm will be suspended if there is less than a 0.10 chance that the treatment failure rate is less than 0.225 for that treatment arm.

The operating characteristics of this study design are summarized in Table 1 below, and are based on 10,000 simulations of the trial for each scenario. From this table we can see that if the true treatment failure rates are 0.2750 and 0.1375 for OO and GP, respectively, then the probability that we will select GP as superior to OO is 0.799, and we expect to be able to reach this conclusion with an average of $35.4 + 61.9 = 97.3$ patients. Also, in this scenario there is only a 0.006 chance that we would select OO as superior to GP, but there is a 0.195 chance that we would conclude that neither treatment is superior to the other.

If the true treatment failure rate is 0.275 for both treatment arms, then the probability that we will select GP as superior to OO is only 0.103, and we expect to be able to reach this conclusion with an average of $48.9 + 49.2 = 98.1$ patients. Also, in this scenario there is a 0.101 chance that we would select OO as superior to GP, but there is a 0.796 chance that we would conclude that neither treatment is superior to the other.

Analysis

Once the trial is completed we will report the probability that GP has a lower treatment failure rate than OO during the late onset phase. We will also estimate the treatment failure rate for each treatment arm during the late onset phase of the first cycle of therapy with a 95% credible interval.

We will estimate with 95% confidence intervals the treatment failure rates for each treatment arm during the first 24 hours (acute phase) and during the 24-72 hour period (delayed phase) of each cycle of therapy. We will similarly estimate the treatment failure rates during the late onset phase for each cycle following cycle 1 of therapy. A treatment success is defined as no emetic or retching episodes and no rescue medication use.

We will tabulate the responses to the 4 items of the Morisky Medication Adherence (Compliance) measure for each treatment group by cycle of therapy. We will compare the 2 treatment groups with respect to the responses to each item of this instrument with a chi-square test. We will use descriptive statistics to summarize the elements of the Morrow Assessment of Nausea and Emesis (MANE Scale) and for pill counts/compliance for each treatment group by cycle of therapy. We will also use repeated measures analysis of variance methods to model compliance over all cycles of therapy.

We will use descriptive statistics to summarize the total scores for the Osoba Module, used to measure the effect of nausea and vomiting on quality of life, for each treatment group by cycle of therapy. We will compare the treatment groups with respect to the Osoba Module score with a Mann-Whitney test. We will also tabulate the responses to each of the 5 questions of the Osoba Module for each treatment group. We will also use repeated measures analysis of variance methods to model the effect of nausea and vomiting on quality of life over all cycles of therapy.

We will use descriptive statistics to summarize the number and amount of dose reductions for each treatment group for each cycle of therapy. We will also use repeated measures analysis of variance methods to model the number and amount of dose reductions over all cycles of therapy. We will similarly analyze the number and doses of rescue medications and the amount of diarrhea experienced over the course of therapy.

Technical Details

We assume a beta (1.1, 2.9) prior distribution for the treatment failure rate for each treatment. This prior distribution has a mean of 0.275 and a standard deviation of 0.200. As the trial progresses these prior distributions will be updated with the data that have accrued.

Let F_{OO} and F_{GP} be the treatment failure rates for treatments “Oral Ondansetron” (OO) and “Granisetron Patch” (GP), respectively. Prior to enrolling the 40th and subsequent patients we will calculate the randomization probability as follows. We will first calculate $\pi_{GP}(\text{data}) = \Pr(F_{GP} < F_{OO} \mid \text{data})$ and $\pi_{OO}(\text{data}) = 1 - \pi_{GP}(\text{data})$. The randomization probability for GP will then be defined as $r_{GP} = \frac{\sqrt{\pi_{GP}}}{\sqrt{\pi_{GP}} + \sqrt{\pi_{OO}}}$, and the randomization probability for OO will be $r_{OO} = 1 - r_{GP}$.

Accrual to treatment arm OO will be suspended if $\Pr(F_{OO} < 0.225 \mid \text{data}) < 0.10$. Similarly, accrual to treatment arm GP will be suspended if $\Pr(F_{GP} < 0.225 \mid \text{data}) < 0.10$. If at any point during the trial $\pi_{GP}(\text{data}) > 0.925$ (< 0.075) the trial will be terminated and treatment “Granisetron Patch” will be selected as superior (inferior). If the maximum number of patients is enrolled in the trial and $\pi_{GP}(\text{data}) > 0.915$ (< 0.085) treatment “Granisetron Patch” will be selected as superior (inferior).

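### Table 1 is not reproduced by the arm-suspension rule as printed, and Section 5.0 gives two different starting points for superiority stopping

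*Combined protocol and SAP*

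**What the plan says.** The main text of Section 5.0 states the suspension rule in one sentence: "accrual to a treatment arm will be suspended if there is less than a 0.10 chance that the treatment failure rate is less than 0.225". The Technical Details part repeats it separately for each arm, beginning "Accrual to treatment arm OO will be suspended if", with the same limits. Neither place says when the check begins, whether the other arm carries on, or whether any selection is made when accrual closes for this reason.

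On superiority, the main text says "Beginning with the 76th patient the trial will be stopped early" when the posterior probability reaches 0.925, and sets the size of the trial: "We will enroll at least 75 and at most 150 patients at an expected rate of 5 patients per month". Technical Details applies the same 0.925 limit with the words "If at any point during the trial". Both use 0.915 at 150 patients.

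The results are introduced with "The operating characteristics of this study design are summarized in Table 1 below", from 10,000 simulated trials per scenario. Under the null (0.275 in both arms) Table 1 gives selection of GP 0.103, of OO 0.101 and of neither 0.796, with 48.9 + 49.2 = 98.1 patients on average. With GP at 0.1375 it gives selection of GP 0.799 and 35.4 + 61.9 = 97.3 patients.

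**The concern.** Table 1 is the only support in the documents for the sample size, the power and the chance of naming a superior arm when there is none. It is useful only if it describes the rules that will be run.

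The suspension rule has a large influence here. A true failure rate of 0.275 lies above the 0.225 limit, so under the null either arm can readily cross. If one arm closes and the other continues, the comparison goes on being examined as far as 150 patients, which adds chances of a false selection. If one closed arm ends the trial, those chances disappear. The text describes closure of one arm and is silent on the trial. The conflict over superiority stopping leaves a second rule open: whether the trial may end below its own minimum of 75.

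**Working it through.** **Inputs (Section 5.0).** Beta(1.1, 2.9) prior per arm. Check: mean 1.1/4.0 = 0.275; SD √(1.1 × 2.9/(16 × 5)) = 0.1997, as stated. With x failures in n patients the posterior is Beta(1.1 + x, 2.9 + n − x). Equal randomization for 40 patients, then r_GP = √π_GP/(√π_GP + √π_OO), where π_GP = Pr(F_GP < F_OO | data). An arm is suspended if Pr(F < 0.225 | data) < 0.10. Superiority at 0.925 from 75/76 and at 0.915 at 150.

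**Assumptions not in the plan.** Outcomes known at once, a look after every patient, and the trial ending if both arms close.

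**Printed target.** Null either-arm selection is 0.101 + 0.103 = 0.204.

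**Rule as printed (only the crossing arm closes), by start of suspension checks:**

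| | Null selection, either arm | Null mean N | Power at 0.1375 |
|---|---|---|---|
| Table 1 | 0.204 | 98.1 | 0.799 |
| From patient 75 | 0.29–0.31 | 112–113 | 0.85 |
| From patient 40 | 0.27–0.28 | 100–102 | 0.84–0.85 |
| From first patient | 0.23–0.24 | 85–86 | 0.82 |

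Ranges are over separate simulations of 2,500 to 20,000 trials per scenario. One 2,500-trial run from patient 40, with no selection when both arms close, gave 0.248. The Monte Carlo standard error of the printed 0.204 is √(0.204 × 0.796/10,000) = 0.004. At 2,500 trials the standard error of 0.24 is √(0.24 × 0.76/2,500) = 0.009.

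**All five scenarios** (OO at 0.275; cells are neither / GP selected / mean N; 20,000 trials for the 75 starts, 10,000 for the 40 start):

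| GP rate | Table 1 | Crossing arm only, from 75 | Crossing arm only, from 40 | Either arm ends trial, from 75 |
|---|---|---|---|---|
| 0.1375 | 0.195 / 0.799 / 97.3 | 0.151 / 0.846 / 95.3 | 0.151 / 0.844 / 93.9 | 0.189 / 0.808 / 94.2 |
| 0.1750 | 0.427 / 0.562 / 106.4 | 0.313 / 0.670 / 107.2 | 0.315 / 0.666 / 104.1 | 0.416 / 0.571 / 103.4 |
| 0.2250 | 0.678 / 0.273 / 107.1 | 0.562 / 0.378 / 116.6 | 0.569 / 0.370 / 109.7 | 0.683 / 0.274 / 105.8 |
| 0.2750 | 0.796 / 0.103 / 98.1 | 0.700 / 0.154 / 112.2 | 0.729 / 0.133 / 101.8 | 0.797 / 0.105 / 97.6 |
| 0.3250 | 0.776 / 0.033 / 88.0 | 0.679 / 0.048 / 100.6 | 0.752 / 0.032 / 88.4 | 0.777 / 0.035 / 86.8 |

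The start at 40 brings mean N near the printed values but not the selection probabilities. About 24% of its null trials end below 75, and the null OO 2.5th percentile is 16 to 20 patients against 26 printed. The start at the first patient has the smallest selection gap, but mean N is too low and the 2.5th percentiles are 2 to 5 patients per arm, where Table 1 shows 21 to 39. Delayed outcomes, looks every 5 patients, reopening a suspended arm, and selecting only while both arms are open do not reproduce the table either.

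**Bound from the printed means, if no trial ends below 75.** The share reaching 150 is at most (mean N − 75)/75. Null: (98.1 − 75)/75 = 0.308, so at least 0.692 end earlier. Taking 0.0927 for both arms, early selection is 0.185, which leaves at least 0.507 ending early without early selection. With checks from 75, closure of both arms supplies about 0.36. This comparison holds only for that start.

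**If either arm's crossing ends the trial, from 75.** Null selection is about 0.19–0.21 (0.182 in one run with no selection at the stop), mean N 97–98 and power 0.79–0.81. The 0.1375 row still does not fit: OO/GP patients 36.9/57.3 against 35.4/61.9, OO 97.5th percentile 77 against 67, and early selection of GP 0.798 against 0.774.

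**Cells in Table 1.** The 0.1750 row sums to 0.4266 + 0.0154 + 0.5620 = 1.0040; the other four sum to 1.0000. Null early selection is 0.0093 for OO beside 0.0927 for GP, although the arms are symmetric there.

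**The case against.** The best reply is that the size of the gap depends on something the plan does not print. The 76th-patient start is attached to superiority stopping; the suspension sentence has no start. A reader might therefore infer from the 75 start alone that the design's false-selection rate is 0.30, or that its mean sample size is understated by 14 patients. The documents support neither as a single figure: mean N may lie above or below 98.1, and with a start at 40 most of that gap goes. What stands is that null selection exceeded 0.204 under every start tried, and that none matched Table 1 across its rows.

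A reader might also infer that the sponsor's program ended the trial when either arm crossed. That rule comes close on selection and total N, but it misses the arm split in the 0.1375 row, and the code is not in the documents. Nor does anything show that the randomization website is wrong.

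On superiority stopping, the specific start and minimum in the main text can be read as governing the general phrase in Technical Details. So the conflict does not show that the trial would be stopped before 75. It is a repair of wording, but it concerns a stopping rule and should be made.

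Finally, the plan sets no limit on false selection or power, so none is breached, and simulated power under the printed rule is above 0.799.

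**Conclusion.** The point holds in conditional form. Run as printed, with the trial ending only when both arms close, the suspension rule gives a null either-arm selection probability of about 0.23 to 0.31, according to when checks start, against 0.204 in Table 1. Null mean N is about 85 to 113 against 98.1, and power about 0.82 to 0.85 against 0.799. These figures rest on immediate outcomes, looks after every patient and superiority stopping from 75/76. With checks from 75, varying the allocation exponent (0.5 or 1), the form of the first 40 allocations and the number of pending outcomes (0 or 2) left null selection at 0.284–0.307. Which rule produced Table 1 cannot be established from the documents. The contradiction on the start of superiority stopping is in the text itself and needs no simulation.

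**What to change.** In Section 5.0, state (a) when suspension is first assessed; (b) what suspension of one arm, and of both, does to the trial; and (c) which cut-off, if any, applies at such a stop. Give superiority stopping one start in both the main text and Technical Details. The one-patient mismatch on adaptive randomization ("Beginning with the 41st patient and as the trial progresses" against "Prior to enrolling the 40th and subsequent patients we will calculate the randomization probability as follows") is immaterial but can be aligned in the same edit.

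Then re-run Table 1 under exactly that text, restate power, mean N and the false-selection rate in either direction, and confirm that the randomization website implements the same rule. In the re-run, correct the 0.1750 row and the null OO early-selection cell.

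The choice of rule is the sponsor's. The cost is a few sentences and one simulation run. If the other arm is meant to continue after a suspension, the stated false-selection rate may become less favourable, at about 0.23 to 0.31. If one suspended arm is meant to end the trial, the headline figures would probably stay near those printed, subject to the re-run.

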1.0 OBJECTIVES

- 1.1 Primary Objective
 - 1.1.1 To measure response rates to anti-emetic therapy (no emetic or retching episodes and no rescue medication use) in the late onset phase (days 4-7) of Granisetron (Sancuso) administered via a transdermal patch compared to orally administered Ondansetron in women with cervical, endometrial or vaginal cancer undergoing chemoradiation therapy.
- 1.2 Secondary Objectives
 - 1.2.1 To measure response rates to anti-emetic therapy (no emetic or retching episodes and no rescue medication use) in the acute (0-24 hours) phase of Granisetron administered via a transdermal patch compared to orally administered Ondansetron in women with cervical, endometrial or vaginal cancer undergoing chemoradiation therapy.
 - 1.2.2 To measure response rates to anti-emetic therapy (no emetic or retching episodes and no rescue medication use) in the delayed (24-72 hours) phase of Granisetron administered via a transdermal patch compared to orally administered Ondansetron in women with cervical, endometrial or vaginal cancer undergoing chemoradiation therapy.
 - 1.2.3 To measure compliance with Granisetron administered via a transdermal patch compared to orally administered Ondansetron in women with cervical endometrial or vaginal cancer undergoing chemoradiation therapy.
 - 1.2.4 To measure amount and effect of nausea/vomiting on quality of life with Granisetron administered via a transdermal patch compared to orally administered Ondansetron in women with cervical endometrial or vaginal cancer undergoing chemoradiation therapy.
 - 1.2.5 To determine if Granisetron administered via a transdermal patch compared to orally administered ondansetron results in less dose reductions of cisplatin in women with cervical, endometrial or vaginal cancer undergoing chemoradiation therapy.
 - 1.2.6 To measure amount of "rescue medication" for chemotherapy-induced nausea and vomiting (CINV) during chemoradiotherapy in women with cervical, endometrial or vaginal cancer undergoing chemoradiation therapy taking Granisetron administered via a transdermal patch compared to orally administered Ondansetron.
- 1.3 Exploratory Objective

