4.2 Duration of treatment

Treatment will last 5 cycles or until the patient withdraws (Section 8.0), whichever comes first. The patient may continue to receive further chemoradiation after 5 cycles at the discretion of the treating physician; however, the patient will be taken off treatment after 5 cycles.

The transdermal patch and Ondansetron should be continued as scheduled even if the IV Cisplatin is held.

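### Acute and delayed response are objectives that compare the arms, but the plan specifies no interval, test, model or probability for the between-arm contrast

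*Combined protocol and SAP*

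**What the plan says.** Section 1.2 words both objectives as comparisons. Objective 1.2.1 concerns response "in the acute (0-24 hours) phase of Granisetron administered via a transdermal patch compared to orally administered Ondansetron", and objective 1.2.2 concerns response "in the delayed (24-72 hours) phase of Granisetron administered via a transdermal patch compared to orally administered Ondansetron". Section 4.3 makes these the first two secondary endpoints, each measured in every cycle.

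The analysis text in section 5.0 reads "We will estimate with 95% confidence intervals the treatment failure rates for each treatment arm" for the acute phase, and the same sentence extends this to failure rates "during the 24-72 hour period (delayed phase) of each cycle of therapy". Late-onset response after the first cycle is handled alike: "We will similarly estimate the treatment failure rates during the late onset phase for each cycle following cycle 1 of therapy".

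The one posterior comparison of the arms in the analysis plan is for the primary phase: "we will report the probability that GP has a lower treatment failure rate than OO during the late onset phase".

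**The concern.** An objective that compares two arms calls for an estimate of the contrast with its uncertainty. Here the prespecified output is one rate and interval per arm, per phase, per cycle. Over five cycles that is five pairs of intervals for each phase.

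Three things follow. The between-arm difference carries no stated precision. Any formal comparison would have to be chosen after the data are seen. The repeated cycles stay as separate cross-sections, although the plan models other endpoints over all cycles. Faced with pairs of intervals, some readers will also look at whether they overlap, which is a much stricter criterion than an interval on the difference.

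**Working it through.** **Text check.** Section 5.0 assigns these methods by endpoint:

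| Endpoint | Between-arm quantity or test | Method over all cycles |
|---|---|---|
| Late-onset response, cycle 1 (primary) | Posterior probability that GP has the lower failure rate | Not applicable |
| Compliance | Chi-square test per Morisky item | Repeated-measures ANOVA |
| Quality of life (Osoba) | Mann-Whitney test | Repeated-measures ANOVA |
| Dose reductions, rescue medication, diarrhea | No separate test named | Repeated-measures ANOVA |
| Acute response | None; per-arm rate and 95% interval | None |
| Delayed response | None; per-arm rate and 95% interval | None |
| Late-onset response after cycle 1 | None; per-arm rate and 95% interval | None |

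No other sentence in section 5.0 supplies a contrast for acute or delayed response. The plan states no power or precision for these comparisons, so there is no figure of its own to reproduce.

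**Inputs for an illustration.** The failure rates 0.275 (OO) and 0.1375 (GP) come from section 5.0. They are design rates for the late-onset primary endpoint and are borrowed here. The average arm sizes 35.4 (OO) and 61.9 (GP) come from Table 1 for that scenario. They are treated as fixed, although allocation and stopping depend on outcomes.

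**Precision of the difference (Wald).**
- SE(OO) = √(0.275 × 0.725 / 35.4) = 0.0750.
- SE(GP) = √(0.1375 × 0.8625 / 61.9) = 0.0438.
- SE(difference) = √(0.0750² + 0.0438²) = 0.0869.
- Half-width = 1.96 × 0.0869 = 0.170.
- GP minus OO = −0.1375, with 95% interval −0.308 to 0.033.
- For the two separate intervals not to overlap, the gap must exceed 1.96 × (0.0750 + 0.0438) = 0.233, against 0.170 for the interval on the difference.

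**Where the two readings part.** Take an assumed 75 per arm, an even split of the maximum of 150, at the same rates. The arm intervals overlap (OO 0.174 to 0.376; GP 0.060 to 0.215), yet the interval for the difference excludes zero (−0.265 to −0.010). This split is for illustration only: in this scenario Table 1 puts the OO arm between 21 and 67 patients.

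**How often each reading would show a difference.** These are exact binomial enumerations with a Wilson interval per arm and a Newcombe interval for the difference.

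| Arms (OO, GP) | True rates (OO, GP) | Intervals do not overlap | Difference interval excludes 0 |
|---|---|---|---|
| 35, 62 | 0.275, 0.1375 | 0.131 | 0.397 |
| 35, 62 | 0.275, 0.275 | 0.006 | 0.050 |
| 35, 62 | 0.275, 0.225 | 0.015 | 0.092 |
| 75, 75 | 0.275, 0.1375 | 0.240 | 0.549 |
| 75, 75 | 0.275, 0.275 | 0.005 | 0.049 |

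**Range for the unknown rates.** With a common failure rate p and arms of 35.4 and 61.9, the half-width is 1.96 × √[p(1 − p)(1/35.4 + 1/61.9)] = 0.413 × √[p(1 − p)]. At p = 0.10 this is 0.124, and at p = 0.50 it is 0.207. The difference would be known to within about 12 to 21 percentage points.

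**The case against.** The strongest reply is that these are secondary endpoints without a power claim, that the objectives set out to measure response rates, and that estimation by arm is a legitimate choice. A reader can subtract one rate from the other. If Wilson limits are reported, a Newcombe interval can even be built from the published output. That stands in part: no information is lost, and it would be too strong to infer that the plan yields no between-arm estimate at all. What is missing is a named contrast with stated uncertainty. A difference with an interval is just as descriptive as two separate rates and adds no claim about significance.

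A reader might also infer that the plan will judge the arms by overlap and so lose two thirds of its power. The documents do not support this, because no overlap rule appears anywhere in them. The percentages describe a possible misreading of the output.

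The rates are open to challenge too. The background in section 2.0 reports no difference between patch and oral granisetron within 72 hours, and its superiority hypothesis for emesis concerns days 4-7. A halving of acute or delayed failure is therefore not what the protocol predicts. With 0.275 against 0.225, even an interval on the difference would exclude zero only about 9% of the time. This weakens the illustration but leaves the gap in the analysis text untouched.

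Lastly, late-onset response after cycle 1 is not a listed endpoint in section 4.3, so per-arm estimates there leave no listed endpoint unanswered.

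**Conclusion.** The concern holds in a limited form. Two objectives worded as comparisons have no specified interval, test, model or probability for the contrast, while compliance and quality of life have both a test and a model over cycles. This rests on the text alone and needs no numerical assumption.

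The figures of about 13% against 40% are illustrative. They assume the late-onset design rates, fixed arms of 35 and 62, and a reader who relies on overlap.

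Two further inferences should be resisted. The primary endpoint is not affected, because it already has a between-arm quantity. Nor does the statement in section 4.2 that study drug "should be continued as scheduled even if the IV Cisplatin is held" justify comparing the arms only in cycles with an infusion. Whether cisplatin is given in later cycles is decided after randomisation and may depend on antiemetic control; objective 1.2.5 itself asks whether the patch leads to fewer cisplatin dose reductions. A main analysis restricted in that way could introduce selection.

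**What to change.** In the analysis part of section 5.0:

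1. For the acute and the delayed phase, report the difference in failure rates (GP minus OO) with a 95% interval at cycle 1, and name the interval method. Keep cycle 1 as the main randomised comparison.
2. Summarise all cycles with one logistic GEE or mixed model per phase, with arm, cycle and arm-by-cycle terms. This matches the repeated-measures approach already planned for compliance and quality of life.
3. Late-onset response in cycles 2-5 may be handled the same way, labelled as supportive.
4. State in advance how cycles with cisplatin held are counted, since the phases are timed from chemotherapy. If an analysis of infused cycles only is wanted, label it a sensitivity analysis.

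The per-arm rates and intervals can stay. The cost is a few lines of text and a little programming, with no new data and no change to the design or the primary analysis.

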4.0 THERAPEUTIC PROGRAM

This phase III study will randomize eligible patients with cervical, endometrial or vaginal cancer undergoing chemoradiation therapy (see above for eligibility criteria) to receive either 34.3 mg of granisetron formulated in a transdermal patch (Sancuso) replaced every 7 days (Group A) **OR** 8 mg of ondansetron orally thrice daily starting with cisplatin administration and continued for 72 hours after chemotherapy infusion (Group B). Patients may not be enrolled on study if they have already started their chemotherapy treatment or have received more than 7 days of radiation prior to starting their chemotherapy.

In addition, data on compliance/ease of administration, amount of nausea and vomiting, and effect of nausea and vomiting on quality of life will also be collected. These data will be collected weekly via self-administered questionnaires that are estimated to take < 5 minutes to complete.

Study Drug and Dosage Schedule

Group A: 34.3 mg of granisetron formulated in a transdermal patch (Sancuso) replaced every 7 days. Patients will have the transdermal patch placed/replaced prior to the IV infusion of cisplatin. At cycle 1, patients will receive IV ondansetron 8mg prior to IV cisplatin. Administration of transdermal patch will be at the start of IV cisplatin. For subsequent cycles, replacement of transdermal patch will start during the premedication period of IV cisplatin.

Group B: 8 mg of ondansetron orally thrice daily starting within 8 hrs of cisplatin administration and continued for 72 hours after chemotherapy infusion.

Cisplatin and premedications will be given per standard order sets and physician discretion.

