4.3 Study Endpoints

Primary Endpoint:

1. The proportion of patients with a complete response (CR; defined as no emetic or retching episodes and no rescue medication use) during the late onset phase (4-7 days post-chemotherapy) measured during cycle 1 of chemoradiation therapy.

Secondary Endpoints:

1. The proportion of patients with a complete response (CR; defined as no emetic or retching episodes and no rescue medication use) during the acute phase (0–24 h post-chemotherapy) measured during each cycle of chemoradiation therapy.
2. The proportion of patients with a complete response (CR; defined as no emetic or retching episodes and no rescue medication use) during the delayed phase (24–72 h post-chemotherapy) measured during each cycle of chemoradiation therapy.
3. Ease of administration/compliance of two medications measured during each cycle of chemoradiation therapy.
4. Effect of nausea/vomiting on quality of life (Osoba Module – Appendix D) measured prior to each cycle of chemoradiation therapy and one week after the last cycle. Amount of nausea/vomiting in the prior week (Morrow Assessment of Nausea and Emesis (MANE Scale) – Appendix C) measured prior each cycle of chemoradiation therapy and one week after the last cycle
5. The number of dose reductions/patient during the 5 week treatment measured prior to each cycle of chemoradiation therapy.

6. The amount of “rescue medications” utilized during the 5 week treatment, including 1 week after the last cycle of cisplatin, measured during each cycle of chemoradiation therapy.

Exploratory Endpoint:

1. The amount of diarrhea experienced weekly by the patient will be graded according to CTC 4.0 and via pill counts of anti-diarrheal medication measured each cycle.

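### The acute and delayed response objectives are worded as comparisons of the two arms, but the plan gives only separate per-arm intervals by cycle, with no between-arm difference and no summary over cycles

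*Combined protocol and SAP*

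**What the plan says.** Section 1.2 words both objectives as comparisons of the arms: response "in the acute (0-24 hours) phase of Granisetron administered via a transdermal patch compared to orally administered Ondansetron" (1.2.1) and response "in the delayed (24-72 hours) phase of Granisetron administered via a transdermal patch compared to orally administered Ondansetron" (1.2.2).

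Section 4.3 defines the matching endpoints "during the acute phase (0–24 h post-chemotherapy) measured during each cycle of chemoradiation therapy" and "during the delayed phase (24–72 h post-chemotherapy) measured during each cycle of chemoradiation therapy". No cycle is singled out. The primary endpoint, by contrast, is fixed "during the late onset phase (4-7 days post-chemotherapy) measured during cycle 1 of chemoradiation therapy". Section 4.2 sets the number of cycles: "Treatment will last 5 cycles or until the patient withdraws (Section 8.0), whichever comes first".

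The Analysis part of section 5.0 gives one method for the two secondary phases: "We will estimate with 95% confidence intervals the treatment failure rates for each treatment arm during the first 24 hours (acute phase", with the same for the delayed phase, in every cycle.

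Section 4.0 adds a feature specific to cycle 1 in its Group A paragraph: "At cycle 1, patients will receive IV ondansetron 8mg prior to IV cisplatin". For later cycles that paragraph describes only replacement of the patch during premedication. The section also leaves cisplatin premedication to standard orders and physician discretion.

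**The concern.** A failure rate with its own interval in each arm does not estimate the difference between arms. The objectives ask how the patch does against oral ondansetron, and the planned output stops one step short of that. It also leaves five cycles per phase with no rule for combining them or for saying which one speaks to the objective.

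The omission stands out because the plan names comparative or longitudinal methods for other outcomes. Acute and delayed response are the first two secondary endpoints, yet they receive less comparative analysis than the exploratory diarrhea endpoint.

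At stake is how clearly the trial can say whether the patch gains or loses control in the first 72 hours. Without a stated contrast, that answer depends on an informal reading of 20 intervals or on a choice of cycle made after the results are known.

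**Working it through.** **1. Methods side by side (section 5.0).**

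| Outcome | Between-arm or longitudinal method named |
|---|---|
| Late-onset response, cycle 1 (primary) | Posterior probability that GP has the lower failure rate |
| Adherence items | Chi-square test |
| Compliance over cycles | Repeated-measures analysis of variance |
| Osoba quality-of-life score | Mann-Whitney test; repeated-measures analysis of variance |
| Dose reductions | Repeated-measures analysis of variance |
| Rescue medication, diarrhea | Analysed in the same way as dose reductions |
| Acute response, delayed response | None: per-arm rate and interval only |

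The sentence that carries the dose-reduction method over to other outcomes covers rescue medication and diarrhea only. It does not reach acute or delayed response.

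**2. Count.** 2 arms x 2 phases x 5 cycles = 20 intervals. A reader who wanted contrasts would have 2 phases x 5 cycles = 10 to choose from.

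**3. Precision of a difference.** The documents give no rate, power or precision for these phases, so there is no figure to reproduce. Inputs:
- Arm sizes 35.4 (OO) and 61.9 (GP): the Table 1 averages when the true late-onset rates are 0.2750 and 0.1375.
- Failure rate 0.30 in both arms: assumed.
- Correlation between cycles in the same patient, rho, 0.3 to 0.7: assumed.

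One cycle: SE = sqrt(0.30 x 0.70 x (1/35.4 + 1/61.9)) = sqrt(0.21 x 0.0444) = 0.0966. Half-width = 1.96 x 0.0966 = 0.189.

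Average of five equally correlated cycles: multiply by sqrt((1 + 4 x rho)/5).
- rho 0.3: 0.189 x 0.663 = 0.126
- rho 0.5: 0.189 x 0.775 = 0.147
- rho 0.7: 0.189 x 0.872 = 0.165

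This takes every patient as contributing all five cycles and ignores the effects of adaptive allocation and early stopping. Missing later cycles would widen the intervals.

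**4. Power under the same assumptions.** For a true difference of 0.10 at two-sided 0.05 (both assumed), power is Phi(0.10/SE - 1.96). One cycle: Phi(1.036 - 1.96) = 0.18. Course average: 0.35 at rho 0.3 and 0.22 at rho 0.7.

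**5. What informal reading would do.** These figures describe readers, not the plan.

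*Overlap of two 95% intervals.* With a common failure rate, non-overlap needs z = 1.96 x (s1 + s2)/sqrt(s1^2 + s2^2), where s = 1/sqrt(n). At 50/50 patients z = 2.77, a two-sided level of 0.0056. At 35.4/61.9 z = 2.75, a level of 0.0060.

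*Choosing among ten contrasts, each read at an assumed 0.05.* If independent, the chance of at least one false positive is 1 - 0.95^10 = 0.40. Integrating over a shared normal factor gives 0.35, 0.29 and 0.21 at correlation 0.3, 0.5 and 0.7.

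**The case against.** The best defence is that the results are meant to be descriptive. Both objectives open as measurement of rates, whereas objective 1.2.5 sets out to determine whether the patch leads to fewer dose reductions. Section 5.0 speaks of comparing where it wants a test and of estimating here. Endpoint and analysis do agree on reporting every cycle. That makes a descriptive purpose legitimate, and it is a reason not to ask for a test. It does not remove the gap: the objectives are still worded as comparisons, nothing labels the endpoints descriptive, and a descriptive comparison still needs a difference with its interval. A reader could compute a one-cycle difference from the published rates and counts. A summary over cycles needs the within-patient correlation, which separate intervals do not show.

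Four stronger readings are tempting and should be resisted.

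- A reader might infer that the plan runs ten unadjusted tests or judges by overlap of intervals. It does neither. The 0.21-0.40 and 0.006 figures are risks of informal reading.
- A reader might infer that these are the only endpoints that show control in the first 72 hours. The MANE and Osoba instruments and rescue use also cover those days, though not phase by phase.
- A reader might infer that cycle 1 should decide, to match the primary. The documents name IV ondansetron for Group A at cycle 1, so the acute contrast there mixes that dose with the patch. What is given in Group B or in later cycles is not fully stated. Cycle 1 is better shown alongside than made decisive.
- A reader might infer that a single contrast would settle the objectives. Under the assumptions above, power for a difference of 0.10 is 0.18 for one cycle and 0.22-0.35 for the course average.

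**Conclusion.** The point holds as a gap in the analysis of two secondary objectives. The plan as written produces no between-arm estimate and no cross-cycle summary for acute or delayed response, although it supplies such methods for other outcomes. That conclusion comes from the text alone.

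The gain from the change rests on assumptions. With a 30% failure rate, 35.4 and 61.9 patients and within-patient correlation 0.3 to 0.7, the half-width falls from about 0.19 for one cycle to about 0.13-0.17 for the course average. That supports estimation, not a powered test. The change should be made, but nothing here bears on the primary result, the adaptive randomization or the stopping rules.

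**What to change.** Add two or three sentences to the Analysis part of section 5.0:

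- For acute and for delayed response separately, report the GP minus OO difference in failure rate with a 95% interval. Take it from one prespecified patient-clustered model over all cycles (GEE or mixed logistic) with cycle as a factor. Say how the model result is turned into a difference in rates.
- Show the cycle 1 difference and the by-cycle arm rates alongside, labelled descriptive. Give the reason: section 4.0 names IV ondansetron for Group A at cycle 1.
- State that these are estimates and that no formal test is powered for either phase.

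The cost is a little more analysis work, with no new data, visits or patients. The downside is that by-cycle differences can no longer be put forward as separate secondary results. The primary endpoint and stopping rules stay as they are.
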